7.1 Test termination points

7.1.1 Relevant definitions

The main objective of the study was to examine the performance of FIT, miR-92a, and FIT + miR-92a for AN. Colonoscopy and histopathology were used as the gold standard to determine the classification of the subject.

Sayooning toot	Colonoscopy and histopathology		
Screening test	Patients	Nonpatients	
Positive	True positive (TP)	False positive (FP)	
Negative	False negative (FN)	True negative (TN)	

When counting the performance of different screening protocols for CRC, subjects with a positive screening test result and a confirmed colonoscopy diagnosis of CRC were counted as true positives, otherwise they were counted as false positives, and subjects with a negative screening test and a confirmed colonoscopy diagnosis of a non-colorectal cancerous lesion, such as a normal, inflamed, polyps, advanced adenoma, or other non-colorectal cancerous lesion were counted as true negatives, otherwise they were counted as false negatives.

When counting the performance of different screening protocols for AN (CRC and AA), a positive screening test with a confirmed colonoscopy diagnosis of CRC or AA was counted as a true positive, otherwise it was counted as a

false positive, and a negative screening test with a confirmed colonoscopy diagnosis of a normal, inflamed, polyps, or other non-colorectal cancerous lesion was counted as a true negative, otherwise it was counted as a false negative.

Specific screening and analysis performance indicators are calculated as follows:

- Sensitivity (SN): also known as true positive rate (TPR), defined as true positive/ (true positive + false negative) × 100%;
- Specificity (SP): also known as true negative rate (TNR), defined as true negative/ (true negative + false positive) × 100%;
- Accuracy (ACC): defined as (true positive + true negative)/ (positive + negative) × 100%;
- Positive predictive value (PPV): defined as true positive/ (true positive + false positive) × 100%;
- Negative predictive value (NPV): defined as true negative/ (true negative + false negative) ×100%.

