7.1.3 Endpoint

The objective of the study is to analyze the performance of FIT, miR-92a and their combination for the detection of AN, evaluating performance indicators such as sensitivity, specificity, predictive values, diagnostic accuracy, likelihood ratios, and overall compliance rate, to formulate a strategy for early screening and prevention of CRC for an average-risk population. Once the project is initiated, the researchers will monitor the progress of enrolment, results of miR-92a and FIT, and colonoscopy and pathology results in real time, and will determine whether to terminate enrolment early based on the number of enrolments and fecal-based miR-92a positivity rate.

Data summaries for all subjects will be summarized in a frequency table:

	Colonoscopy	and/or histopatholog	T. 4-1	
Test result	CRC	AA	NEG	Total
Positive	a	b	c	a+b+c
Negative	d	e	f	d + e + f
Total	a + d	b + e	c + f	N

CRC colorectal cancer, AA advanced adenomas, NEG negative (including polyps, other non-colorectal cancerous lesion and no findings)

- (1) The sensitivity and specificity will be calculated as:
- xx test sensitivity for subjects with CRC = a/(a + d)
- xx test sensitivity for subjects with AA = b/(b + e)
- xx test sensitivity for subjects with AN = (a + b)/(d + e)
- xx test specificity for subjects with negative findings = f/(c + f)
- (2) The PPV and NPV will be calculated as:
- PPV (CRC) = Probability of having CRC given a positive xx test result = a/(a + b + c)
- PPV (AA) = Probability of having AA given a positive xx test result = b/(a + b + c)
- PPV (AN) = Probability of having AN given a positive xx test result = (a + b)/(a + b + c)
- NPV = Probability of having negative findings on colonoscopy given a negative xx test result = f/(d + e + f)
- (3) The LRs will be calculated as:
- PLR (CRC) = P (Test positive | CRC)/P (test positive | No CRC) = a/(b+c)
- PLR (AA) = P (Test positive | AA)/P (test positive | No AA) = b/(a + c)
- PLR (AN) = P (Test positive | AA or CRC)/P (test positive | No AA nor CRC) = (a + b)/c
- NLR (NEG) = P (Test negative | NEG)/P (test negative | AA or CRC) = f/(d + e)

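### All four likelihood-ratio count formulas in Protocol 7.1.3 drop the column totals, and the negative ratio is also the reciprocal of the conventional one

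*Protocol*

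**What the plan says.** Section 7.1.3 sets out one table per test: "Data summaries for all subjects will be summarized in a frequency table". Its columns are CRC, AA and NEG. The positive row is a, b, c and the negative row is d, e, f, so the letters are counts. NEG is glossed as "NEG negative (including polyps, other non-colorectal cancerous lesion and no findings" (closing bracket cut).

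The list under the table then gives the calculation for each likelihood ratio (LR). Three of these quotes also lose a closing bracket:

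- Advanced neoplasia, the target of the study's main objective, has the line "PLR (AN) = P (Test positive | AA or CRC)/P (test positive | No AA nor CRC) = (a + b)/c".
- Cancer alone is handled in the same style, by "PLR (CRC) = P (Test positive | CRC)/P (test positive | No CRC) = a/(b+c".
- The only negative ratio on offer is given as "NLR (NEG) = P (Test negative | NEG)/P (test negative | AA or CRC) = f/(d + e".
- Adenoma alone completes the set, with "PLR (AA) = P (Test positive | AA)/P (test positive | No AA) = b/(a + c".

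The same list gives sensitivities for CRC, AA and AN, with the AN line written as (a+b)/(d+e). It gives a single specificity, "xx test specificity for subjects with negative findings = f/(c + f", and a single NPV, f/(d+e+f), described as the chance of negative findings after a negative test.

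Section 7.1.1 defines the CRC classification separately. Among test-negative subjects, "polyps, advanced adenoma, or other non-colorectal cancerous lesion were counted as true negatives", and any positive test without CRC is a false positive. Section 7.2 names likelihood ratios among the main measures for AN.

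**The concern.** A likelihood ratio compares two conditional probabilities, each with its own denominator. Every line in 7.1.3 states such a ratio and then sets it equal to one count divided by another. The two sides would agree only if the diseased and comparison columns held equal numbers, and 5.5 assumes 0.3% CRC and 3% AA.

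The list prescribes the calculation, and likelihood ratios are among the main measures. An analyst who follows it would report, for a test with the assumed performance, positive ratios well below 1. A reader would take a positive result as evidence against disease. The figures would also move with prevalence, which a likelihood ratio is meant to avoid.

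**Working it through.** **Inputs (Protocol 5.5).** CRC prevalence 0.3%, AA prevalence 3%; miR-92a sensitivity 90% for CRC and 80% for AA; specificity 90%; W = 0.09. The protocol states no numerical LR, so the figure to reproduce is the sample size: 1.96² × 0.9 × 0.1 / 0.09² = 42.68, and 42.68 / 0.003 = 14,228, as stated.

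**Algebra.** With counts a to f, P(T+ | CRC) = a/(a+d) and P(T+ | no CRC) = (b+c)/(b+c+e+f). Their ratio is a/(b+c) multiplied by (b+c+e+f)/(a+d), the odds of not having CRC. The plan omits that factor. From the plan's own PPV(CRC) = a/(a+b+c), it follows that PPV/(1−PPV) = a/(b+c), so the printed expression is the post-test odds. The AA and AN lines behave in the same way.

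**A choice that must be stated.** Section 5.5 gives 90% specificity for CRC and again for AA without fixing the comparator. Two readings are shown.

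- Reading 1 applies 90% to the NEG column only.
- Reading 2 applies 90% to all non-CRC subjects. The NEG specificity is then (0.9 × 0.997 − 0.03 × 0.2)/0.967 = 92.2%.

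**Expected cells at N = 14,228.** Under both readings a = 38.4, d = 4.3, b = 341.5 and e = 85.4. Reading 1 has c = 1,375.8 and f = 12,382.6. Reading 2 has c = 1,077.1 and f = 12,681.4.

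**Reading 1, step by step.**

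- PLR(CRC): written 38.4/(341.5 + 1,375.8) = 0.022. With column totals, 0.90/(1,717.3/14,185.3) = 7.43.
- PLR(AA): written 341.5/(38.4 + 1,375.8) = 0.241. With column totals, 0.80/(1,414.3/13,801.2) = 7.81.
- PLR(AN): written 379.9/1,375.8 = 0.276. With column totals, (379.9/469.5)/(1,375.8/13,758.5) = 0.809/0.100 = 8.09.
- Negative ratio: written 12,382.6/89.6 = 138.1. On its own probability wording, 0.900/(89.6/469.5) = 4.71. By the conventional definition, (89.6/469.5)/0.900 = 0.212, which is 1/4.71.

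**Both readings.**

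| Quantity | As written | With column totals |
|---|---|---|
| PLR(CRC) | 0.022 / 0.027 | 7.43 / 9.00 |
| PLR(AA) | 0.241 / 0.306 | 7.81 / 9.90 |
| PLR(AN) | 0.276 / 0.353 | 8.09 / 10.34 |
| Negative ratio, own wording | 138.1 / 141.5 | 4.71 / 4.83 |
| Negative ratio, conventional | not given | 0.212 / 0.207 |

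The missing factor depends only on the column totals: 14,185.3/42.7 = 332 for CRC, 13,801.2/426.8 = 32 for AA, and 13,758.5/469.5 = 29 for AN and for the negative ratio on its own wording.

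**AN sensitivity in the same list.** (a+b)/(d+e) = 379.9/89.6 = 4.24, or 424%. With the diseased total in the denominator, 379.9/469.5 = 80.9%.

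**CRC comparator.** Section 7.1.1 implies CRC specificity (e+f)/(b+c+e+f), which is 87.9% (reading 1) or 90.0% (reading 2). The one specificity in 7.1.3, f/(c+f), is 90.0% or 92.2%. For NPV under reading 1, (e+f)/(d+e+f) = 99.97% and f/(d+e+f) = 99.28%.

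**The case against.** The best defence is that the probability part of each positive ratio is correct and printed beside the count expression, so the intended quantity can be recovered and standard software would compute it properly. The first half is true. But the count expression is what the list tells the analyst to compute, and all four lines share the fault, so it is not an isolated slip.

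The label on the negative ratio suggests that a likelihood ratio for being disease-free may have been meant. On that reading the inversion is only a departure from convention. The gap between 138 and 0.21 therefore mixes two things: the dropped totals (138 against 4.71) and the reciprocal (4.71 against 0.212). The count expression fails even on the disease-free reading.

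A reader might infer that 7.1.1 and 7.1.3 define CRC specificity in two contradictory ways. The documents do not support that. The specificity and NPV in 7.1.3 are labelled for negative findings, not for CRC, and for AN the two sections agree. PLR(CRC) in 7.1.3 also conditions on the absence of CRC, the same comparator as 7.1.1. What stands is an omission: 7.1.3 lists a CRC sensitivity but no CRC specificity or NPV. An analyst who pairs that sensitivity with the only specificity listed would get 0.90/0.10 = 9.0 under reading 1, where the stated comparator gives 7.43.

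The sizes also assume that every subject is classified. If the table held all test positives and an equal number of test negatives, unweighted, PLR(AN) would be 0.276 as written and 2.19 with column totals. The factor shrinks, but the expression is still wrong.

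**Conclusion.** The point holds for all four likelihood-ratio expressions. It follows by algebra from 7.1.3 alone, and the sizes rest on the 5.5 assumptions under the two specificity readings. PLR(CRC) is 0.022 to 0.027 as written against 7.4 to 9.0; PLR(AA) 0.24 to 0.31 against 7.8 to 9.9; PLR(AN) 0.28 to 0.35 against 8.1 to 10.3. The negative ratio is 138 to 142 against 4.7 to 4.8 on its own wording and 0.21 by convention. Because likelihood ratios are among the main measures, this must be corrected.

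The CRC comparator is a secondary matter of clarity, worth about 2 percentage points of specificity. A reader might also suppose that the sample size is affected. It is not: the calculation in 5.5 uses no likelihood ratio.

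**What to change.** In 7.1.3, replace the count expressions as follows:

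- PLR(CRC) = [a/(a+d)] / [(b+c)/(b+c+e+f)]
- PLR(AA) = [b/(b+e)] / [(a+c)/(a+c+d+f)]
- PLR(AN) = [(a+b)/(a+b+d+e)] / [c/(c+f)]
- NLR(AN) = [(d+e)/(a+b+d+e)] / [f/(c+f)]

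Correct AN sensitivity to (a+b)/(a+b+d+e), since the AN ratios depend on it. Label f/(c+f) and f/(d+e+f) as the AN specificity and NPV. Add CRC lines with the comparator of 7.1.1: specificity (e+f)/(b+c+e+f) and NPV (e+f)/(d+e+f), so that CRC specificity, NPV and PLR share one comparator.

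The cost is a text correction. Any ratios already computed from the printed expressions can be recomputed from the same six counts. No new data and no change to the sample size are needed.

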7.2 Analysis of clinical outcomes

The main indicators for the analysis of clinical results were the sensitivity, specificity, predictive values, diagnostic accuracy and likelihood ratios of FIT, miR-92a, and their combination in screening AN, using the results of colonoscopy and histopathology examination as the gold standard. The data were analyzed using SAS, SPSS, Stata or other commonly used clinical research data analysis software to obtain the best cut-off value.

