2.2 Fecal miR-92a detection technology

We has previously completed clinical trials in Shenzhen People's Hospital, Guangzhou Sun Yat-sen University Cancer Prevention and Treatment Centre and Tianjin People's Hospital for its miR-92a test based on stool samples. The product was approved for marketing by the National Medical Products Administration (NMPA) in March 2018 (National Machinery Registration Standard 20183400108) through the national innovative medical device special approval channel. A total of 1306 clinical subjects were enrolled in the pre-market clinical trial, including 340 cases of confirmed colorectal

cancer, 901 cases of confirmed non-colorectal cancer, including esophageal cancer, gastric cancer, hepatocellular cancer, pancreatic cancer, cholangiocarcinoma, oral cancer, gastritis, enteritis, appendicitis and peptic ulcer, 901 cases of patients with colorectal polyps and adenomas, as well as a control group of the normal population, and 65 cases of patients with post-surgery CRC.

The expression of miR-92a in the intestinal epithelial cells of CRC patients increases with the onset of the disease. Consequently, the detection of miR-92a in exfoliated intestinal epithelial cells obtained from fecal samples serves as an effective tool for identifying the risk of colorectal cancer (CRC), including pre-cancerous polyps, adenomas, and other related lesions. Stool miR-92a was detected by extracting total RNA from stool samples using a nucleic acid extraction reagent and performing miR-92a-specific RT-PCR reaction. The primers and probes in the reaction solution are designed to specifically bind to and amplify miR-92a and its reverse transcription product. Compared to colonoscopy, the fecal-based miR-92a assay demonstrates high sensitivity and specificity in detecting CRC and precancerous lesions like adenomas. It functions as a potent screening tool for identifying individuals at risk for CRC, and facilitates comprehensive screening and diagnosis of CRC and precancerous lesions, notably adenomas in their advanced stages.

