4.2.4 Procedure

Fecal-based miR-92a test uses nucleic acid extraction reagents to extract total RNA from stool samples and perform

miR-92a-specific RT-PCR on them.

The primers and probes in the reaction solution can bind to and amplify miR-92a and its reverse transcription

products.

During the amplification process, once the probe complements and binds to the reverse transcription cDNA strand

containing the miR-92a template, the fluorescent dye group positioned at the 5' end of the probe is cleaved by the

Taq-enzyme, resulting in the release of fluorescent signals.

The fluorescence signal released by the probe is monitored by a quantitative fluorescence PCR instrument in real

time and a curve is generated to reflect the miR-92a content in the sample.

Results determination:

a. Positive: The Ct value of the sample to be tested is < 32.00.

b. Negative: The Ct value of the sample to be tested is ≥ 32.00 .

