4.3.4 Procedure

- Leave the reagent at room temperature for 30 min before use and return to room temperature (20 − 30 °C). Do not open the inner package until it is ready for use, and use it within 1 hour after opening the inner package (humidity: 20 − 90%, temperature: 10 − 50 °C).
- Add 1 ml of distilled won water to the fecal specimen and mix well for examination.
- Open the inner package, take out the reagent and put it on the countertop.
- Add 2 drops of diluted sample (approximately 80 ml) vertically to the reagent spiking tip and observe the result within 5 min, after which the result is invalid.
- Results determination:
 - a. Positive: A red line appears at each of the test line (T line) and control line (C line).
 - b. Negative: A red line appears at the C line only.
 - c. Invalid: The absence of a red line at the C line indicates an operational error or reagent failure.

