5.5 Sample size considerations

The required sample size for the test is based on the following assumptions:

The ratio of AA to CRC in general risk population is 10:1;

Among the population aged 30 - 75, approximately 30 out of every 10,000 people are patients with CRC and 300 out of every 10,000 people are patients with AA;

The sensitivity and specificity of fecal-based miR-92a detection for CRC are 90% and 90%, respectively. The sensitivity and specificity of fecal-based miR-92a detection for AA are 80% and 90%, respectively;

The sample dropout rate is 5%.

According to the Buderer formula [13], the required sample size is estimated as follows:

Step1: Specifications

SN: sensitivity; SP: specificity; 1- α : confidence level; $Z_{1-\alpha/2}$: standard normal deviation (when $\alpha = 0.05$, $Z_{1-\alpha/2} = 1.96$); W: allowable error, set to 0.09 here; Prevalence: prevalence rate, which is the ratio of positive cases in all samples. We set the prevalence rate for CRC to be 0.3% and the prevalence rate for AA to be 3%.

Step2: Calculate the number with disease, TP + FN

TP + FN =
$$Z_{1-\alpha/2}^2 \frac{SN(1-SN)}{W^2}$$

Step3: Calculate the sample size required for sensitivity, N₁

$$N_1 = \frac{TP + FN}{P}$$

For CRC, $N_1 = 14,228$; for AA, $N_1' = 2,529$

Step4: Calculate the number without disease

$$FP + TN = Z_{1-\alpha/2}^{2} \frac{SP(1 - SP)}{W^{2}}$$

Step5: Calculate the sample size required for specificity, N2

$$N_2 = \frac{FP + TN}{1 - P}$$

For CRC, $N_2 = 43$; for AA, $N_2' = 78$

Step6: Select the final sample size, N

$$N = 14,228$$

In summary, considering a 5% dropout rate, the required sample size is 14,975. To ensure sufficient sample size after excluding unqualified samples, 15,586 individuals were ultimately included in this study.

6. Research program design and processes

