7.4 Statistical methods

A variety of categorical data analysis methods will be used to analyze the results from the miR-92a, FIT and FIT + miR-92a results. Binomial proportions and exact 95% CI summarize sensitivity and specificity across categories. According to the study design, FIT and miR-92a from the same subjects were considered as a paired design, and the exact McNemar's test was used to compare the differences of DR, PR, Se and Sp between these two groups. Given the susceptibility of PPV to confounding factors like prevalence and subject characteristics, the GEE (Generalized Estimating Equations), which is based on McNemar's test, was utilized to compare the differences in PPV between the two groups.

8. Ethical issues

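### Section 4.2.4 fixes miR-92a positivity at Ct < 32.00, but section 7.2 adds a search for a best cut-off without saying which threshold the reported accuracy uses

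*Protocol*

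**What the plan says.** Section 4.2.4 gives a complete binary rule for the miR-92a assay. A low Ct counts as a positive result: "Positive: The Ct value of the sample to be tested is < 32.00". At or above the same value the result is reversed: "Negative: The Ct value of the sample to be tested is ≥ 32.00". Section 2.2 describes an established product: "The product was approved for marketing by the National Medical Products Administration (NMPA) in March 2018".

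Section 7.2 opens the clinical analysis: "The main indicators for the analysis of clinical results were the sensitivity, specificity, predictive values, diagnostic accuracy and likelihood ratios". These apply to each stool test alone and to the two together, with AN as the target. The next sentence lists software packages and ends "or other commonly used clinical research data analysis software to obtain the best cut-off value". It names no test, no criterion for best and no validation step. It does not say whether the derived value is to be used for the main indicators.

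Section 7.4 sets the inference: "Binomial proportions and exact 95% CI summarize sensitivity and specificity across categories". It adds exact McNemar tests for the paired FIT versus miR-92a comparison, and GEE for PPV.

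**The concern.** Only one numeric threshold in the protocol could be searched. FIT is qualitative (section 4.3.4: a line appears or it does not), so the clause in 7.2 can only concern the miR-92a Ct value.

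A cut-off chosen to look best in a set of subjects looks better in those subjects than it will in new ones. The exact binomial intervals and McNemar tests of section 7.4 treat the positivity rule as given in advance, so they make no allowance for the choice. The effect would also be one-sided: miR-92a, and the combination that contains it, could gain from tuning, while FIT could not. CRC sensitivity is the most exposed because it rests on the fewest cases, and it is also the quantity that drives the sample size in section 5.5.

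**Working it through.** **1. The passages side by side.**

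| Place | Threshold used |
|---|---|
| 4.2.4 | Ct < 32.00, fixed |
| 6.6 (who is referred for colonoscopy) | positive/negative result, fixed |
| 7.1.1 and 7.1.3 (all formulas) | positive/negative result, fixed |
| 7.2 | a best cut-off, to be obtained from the data |
| 7.4 | methods that assume a fixed rule |

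No sentence links the derived cut-off to the formulas, and none keeps it apart from them.

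**2. Case numbers from the plan's own figures (section 5.5).** Inputs: Z = 1.96, W = 0.09; sensitivity 90% (CRC) and 80% (AA); specificity 90%; prevalence 0.3% and 3%.

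- CRC cases = 1.96² × 0.90 × 0.10 / 0.09² = 42.68; N = 42.68 / 0.003 = 14,228, which reproduces the stated figure.
- AA cases = 1.96² × 0.80 × 0.20 / 0.09² = 75.88; N = 75.88 / 0.03 = 2,529, also as stated.
- Rounded up, 43 CRC plus 76 AA cases gives 119 AN cases.
- Expected AN cases if all 14,228 were verified: 14,228 × 0.033 = 469.5, about 470.

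**3. Size of the optimism.** Two assumptions are needed because the protocol supplies neither: Ct values follow an equal-variance binormal model, and best means the largest sensitivity + specificity (Youden). Non-cases are N(0, 1) and cases N(μ, 1), with μ set so that one cut-off gives the assumed sensitivity and specificity: μ = 1.28 + 1.28 = 2.56 for 90/90, and μ = 1.28 + 0.84 = 2.12 for 80/90. In each of 2,000 simulated data sets the Youden cut-off was chosen in the sample. Its apparent sensitivity was then compared with its true sensitivity.

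| Setting (cases / non-cases) | Apparent sensitivity | True sensitivity at chosen cut-off | Optimism (points) | Coverage of exact 95% CI, tuned | Coverage, fixed cut-off |
|---|---|---|---|---|---|
| CRC, 43 / 1,000, 90/90 | 92.1% | 88.3% | 3.8 | 94.3% | 96.5% |
| CRC, 43 / 5,000, 90/90 | 92.5% | 88.5% | 4.0 | 93.4% | 96.4% |
| AN, 119 / 2,000, 80/90 | 87.1% | 84.7% | 2.5 | 91.6% | 96.2% |
| AN, 400 / 3,000, 80/90 | 86.2% | 85.1% | 1.1 | 93.3% | 96.5% |

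Separate runs with 470 AN cases gave 0.9 to 1.0 points. Runs with 43 CRC cases and up to 13,758 non-cases gave 4.0 to 4.4 points. With the cut-off fixed in advance, the bias in the tabulated settings was 0.2 points or less.

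The last column but two is the optimism alone. In the AN rows, most of the rise from the assumed 80% to about 86% is a real change of operating point, paid for in specificity: the true Youden optimum at μ = 2.12 has sensitivity and specificity of about 85.6% each. That shift is not bias, but it is another reason why a reader must know which threshold was used.

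**The case against.** The strongest reply is that the search rests on one trailing clause in a sentence about software. Everything operational uses a fixed positive or negative result: the assay rule, the referral to colonoscopy, every formula in section 7.1, and the tests in section 7.4. No listed endpoint needs a derived cut-off. The clause may be loose wording. A secondary look at thresholds would not strictly conflict with a fixed operating rule, and it could serve the stated aim of forming a screening strategy. All of this stands, and it limits the point to an unresolved ambiguity.

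Three stronger readings are tempting and are not supported:

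- **That the plan will report a tuned cut-off, or has two competing headline results.** The protocol never says that a derived cut-off supplies the main result.
- **That the 4-point figure describes the main result.** It applies to CRC alone. The main indicators concern AN, where the figure is about 1 point with 400 to 470 cases. All the tabulated values are below the allowable error of 9 points, and interval coverage falls only modestly.
- **That partial verification makes this a defect of the search.** Sampling test-negatives for colonoscopy affects accuracy at Ct 32.00 as well, and FIT-positive subjects with Ct at or above 32.00 are also referred. Removing the search would not cure it, so it is a separate matter.

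A statistical analysis plan, not shown here, may settle the threshold. That does not dispose of the point, because the protocol does more than leave a detail open: it states a data-driven step beside a fixed rule.

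**Conclusion.** The point holds as an ambiguity to be resolved, with a bias that is conditional and modest. The protocol fixes Ct < 32.00, states a search for a best cut-off directly after the main indicators, and does not say which threshold the reported accuracy uses. If the tuned value were the headline, miR-92a sensitivity would be overstated by about 1 point for AN with 400 to 470 cases, about 2.5 points with 119, and about 4 points for CRC with 43. The paired sensitivity comparison with FIT would lean the same way. At 43 CRC cases the optimism is a little under half of the allowable error of 9 points.

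These sizes rest on the assumed binormal model and Youden criterion, and on random samples of verified cases and non-cases. The number of verified non-cases matters little (3.8 points with 1,000, 4.0 with 5,000); the number of verified cases matters most. Partial verification is not included.

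**What to change.** In section 7.2, state that all main indicators, their exact confidence intervals, and the McNemar and GEE comparisons use the pre-specified Ct < 32.00. Then either delete the cut-off clause or label any cut-off search exploratory. If it is kept, name the criterion, report optimism-corrected sensitivity and specificity (cross-validated or bootstrap), and never present the result as the headline.

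This is a change of wording only, with no effect on conduct, sample size or data collection. The sponsor gives up the option of a tuned headline cut-off.
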